## 6. Study Timelines

6.1. The estimated total of duration of the study is 18 months. Participants will be followed for 24 weeks (please see timeline below and further specific details on data collection in Section 12). Enrollment is estimated to start at the beginning of 2019. All participants will be recruited within a one-year time frame. The research project will conclude once all enrolled participants have been followed for 6 months and completed the questionnaires. Primary analyses will begin once all study participant complete the 8 weeks follow-up to accomplish the analysis for the primary outcomes.

\* primary outcomes

PROTOCOL TITLE: Effect of immediate versus standard postpartum insertion of the contraceptive implant on breastfeeding outcomes

## 7. Study Endpoints

	Screen -ing	First 24 hours Post partu m	1-7 days*	2 weeks	4 weeks	6 weeks	8 weeks	12 weeks	24 weeks END	Up to 1 year pp	Up to 5 years pp
Intake	X										
Postpartum contraception counseling satisfaction survey	X				X						
Device Insert		X			X	X					
Exclusive breastfeeding			X	X	X		X	X	X		
Breastfeeding discontinuation				X	X		X	X	X		
Retrospective Breastfeeding Discontinuation Chart Review Form										X	
Contraceptive use			X		X		X	X	X		X
Diary collection				X	X		X				
Mood (EPDS)				X	X		X				
Sexual function (FSFI)					X		X	X			
Bleeding log review				X	X		X				

7.1. The primary endpoint of this research are to compare continuation of lactation at eight week postpartum between women in the immediate with standard group.

The secondary endpoints of this research are to compare number of days of postpartum bleeding, postpartum sexual function as measured by FSFI score, and postpartum mood as measured by EPDS score, time to resumption of sexual activity, exclusive breastfeeding method, factors associated with discontinuing breastfeeding, timing of breastfeeding discontinuation, patient satisfaction with postpartum contraception counseling and the implant and patient satisfaction with bleeding pattern between the immediate and standard insertion groups.

As in other studies of breastfeeding and hormonal contraception, we will continue to follow women out to 6 months. A survival analysis will be performed to determine longer-term effect of hormonal contraception on breastfeeding.

**PROTOCOL TITLE:** Effect of immediate versus standard postpartum insertion of the contraceptive implant on breastfeeding outcomes

- 7.2. The primary study endpoint is also a safety endpoint: breastfeeding continuation through 8 weeks. We have developed a Data Safety and Monitoring Plan related to these endpoints (please see below).
- 7.3. No exploratory endpoints will be conducted in this research.

## **8. Research Setting**

- 8.1. Our study will be conducted at multiple clinical sites: the University of New Mexico Hospital, its affiliated clinics and the University of Utah Hospital and its affiliated clinics. These clinical sites are well versed in managing the competing demands of a busy clinical schedule and robust research. This site is part of a Clinical Translational Science Center and the project will be overseen by the University of New Mexico Department of Obstetrics and Gynecology, Family Planning Division with contribution to patient recruitment from the Division of Midwifery and the Department of Family and Community Medicine. The primary investigator of the study is [name] and the faculty mentors are [name] and [name] at UNM and [name] at the University of Utah. Progress on the project will also be followed by the Fellowship in Family Planning as part of fellowship graduation requirements.
- 8.2 Patients may be recruited in the following locations/timeframes: 1) antenatal clinics, 2) visits to OB-Triage 2) on admission to L&D for delivery not in active labor or 4) during the first postpartum hours in the Ob-Gyn ward of the UNM and Utah's Hospital. Recruitment may occur remotely.
- 8.2. The implant insertions will be performed in the UNM Hospital and the University of Utah Hospital for immediate insertion group and in the affiliated clinics for the standard insertion group

Recruitment and research procedure locations:

UNM's Labor and Delivery UNM Westside Clinic UNM Northeast Heights Clinic UNM Southeast Heights Clinic Los Lunas First Choice UNM Women's Health Clinic	UNM Faculty and Midwife Clinic UNM Maternity and Family Planning Clinics UNM Center for Reproductive Health UNM Triage/ OB Special Care Units UNM Family Practice Center / Tucker First Nations Clinic
Utah's Labor and Delivery Utah's associated clinics	

- 8.4. No community advisory board will participate in this study.
- 8.5. No research will be conducted outside of UNM HSC and its affiliates.

## **9. Resources Available**

**PROTOCOL TITLE: Effect of immediate versus standard postpartum insertion of the contraceptive implant on breastfeeding outcomes**

- 9.1. The PI is a board certified obstetrician-gynecologist with subspecialty training in Family Planning. She has a Master of Science in Clinical Research and was the PI on a 600-participant cohort study that was published in a leading OBGYN peer reviewed journal. She recently published an analysis of immediate postpartum contraceptive implant initiation and breastfeeding continuation. [name] spent the previous two years working on the US MEC as a guest researcher. In that role, she presented the data behind CDC's hormonal contraception and breastfeeding recommendations at the Academy of Breastfeeding Medicine's Annual Meeting 2017 and at Grand Rounds for the Medical University of South Carolina in 2018. Also, the Family Planning Research team at the University of New Mexico has successfully conducted a similar RCT of early versus standard insertion of levonorgestrel IUD and impact on breastfeeding. Similar enrollment and data collection policies will be employed for this study.
- 9.2. All licensed physicians/providers who will be inserting the implant are responsible for medical decision-making, ordering, and evaluation of necessary diagnostics and therapeutics.
- 9.3. There are ample patients available to participate in this trial as approximately 200 of the 3000 women who deliver at the University of New Mexico have the ENG implant for postpartum contraception inserted before being discharged after delivery. The time that will be devoted to conducting and completing the research is 18 months. The research will be conducted at the UNM Hospital and its affiliated clinics and University of Utah Hospital and its affiliated clinics. The UNM and University of Utah systems have available medical and psychological resources for participants that might need it as a result of an anticipated consequences of the human research. In addition, all persons assisting with the research will be adequately informed about the protocol, the research procedures, and their duties and function through a process of training

## **10. Prior Approvals**

- 10.1. The national office for the Fellowship in Family Planning approved the research as part for the requirement for completion of the fellowship.
- 10.2. See attachment.
- 10.3. No ionizing radiation will be used in this study.
- 10.4. No biological specimen will be collected for this study.

## **11. Multi-Site Research**

- 11.1. UNM is the lead coordinating site and [name] is the lead investigator. This will be a multi-site study in which University of Utah will be an external site for recruitment of participants. All sites have the most current version of the protocol, consent document and HIPAA authorization. All required approvals will be obtained by the UNM IRB and University of Utah's IRB.

**PROTOCOL TITLE:** Effect of immediate versus standard postpartum insertion of the contraceptive implant on breastfeeding outcomes

The University of Utah will have their side of the study reviewed by the University of Utah IRB and the University of New Mexico will have the UNM IRB reviewing this protocol. The only exchange of patient information is from the University of Utah to the University of New Mexico. All modifications will be communicated to the external sites and approved before the modifications are implemented. All engaged participating sites will safeguard data as required by local information security policies. All local site investigators will conduct the study appropriately. All non-compliance with the study protocol or applicable requirements will be reported in accordance with local policy.

11.2. We will have regularly scheduled contact bi-monthly and potentially monthly as the research progresses to ensure that any adverse events, problems, interim results, data monitoring, and closure of a study are communicated.

11.3. NA. This is not an FDA regulated trial

## **12. Study Procedures**

### 12.1 NA

12.2 Patients may be recruited in the following locations/timeframes: 1) antenatal clinics, 2) visits to OB-Triage 2) on admission to L&D for delivery not in active labor or 4) during the first postpartum hours in the Ob-Gyn ward of the UNM Hospital and University of Utah Hospital and its associated clinics.

- Patients may be asked for their contraceptive choice in any of these four venues, although ideally in antenatal clinics during prenatal care. When women decide on an implant as a postpartum contraceptive in any of these venues, the PCP (Ob-Gyn, Family Medicine physicians/residents and midwives) may discuss the patient's interest in hearing about the study and may contact the research coordinator by a message in the EMR or by phone or in person to let her know that the patient is interested in hearing about the study.
- Additionally, the research coordinator will review antenatal clinic, OB Triage and inpatient (L&D and postpartum) lists to assess patients' contraceptive plan through review of the EMR. The research coordinator may contact patients who have decided on a postpartum implant to assess her interest in participating in the study.
- If the patient expresses interest, the research coordinator will present the study and ask the patient for her interest in enrolling. If interested, the research coordinator and/or a study co-investigator will explain the study, screen for eligibility and obtain informed consent. Participants can also be consented remotely by phone call or via zoom conference. In the case of remote consent, we will obtain written consent via e-mail or mail due to the current pandemic and research coordinators working from home. We will also allow participants to consent via e-signature via the eConsent feature in the UNM HSC REDCap system if they have that capability. The screen for eligibility will be done by interview and assessment of past medical history with standardized set of questions.

**PROTOCOL TITLE:** Effect of immediate versus standard postpartum insertion of the contraceptive implant on breastfeeding outcomes

- Women will not be approached for study participation if they are in active labor. Women will be approached and enrolled, if interested, either prior to active labor (e.g., when admitted for induction of labor or scheduled cesarean delivery) or after delivery.
- Once the woman is enrolled in the study a line will be added to the Antenatal Supplemental Visit Form stipulating the patient's participation in the study and the coordinator's phone number: Ex: "[name] study patient – page at admission ####-#####\*\*." This Form is a section of the EMR that is updated at each visit by the clinic provider with important/current antenatal issues; it is standard that the contraceptive plan for each patient is recorded here.

*Identification of study patients on L&D*

- The PCP on L&D may identify study patients who self-identify as being in the study. They will also be alerted by the "Study Patient" in the antepartum record if the patient has been enrolled antepartum. They will notify the research coordinator who will carry a phone during working hours.
- A reproductive health on-call fellow/attending will be designated 24-7 to ensure randomization and implant insertion within 24 hours for those randomized to the immediate group. After hours (nights and weekends), the research cell will forward to the reproductive health on-call fellow or attending. In addition, the voice message for the research cell will direct callers to contact the reproductive health on-call fellow through Amion, the hospital online paging system. A calendar will specify which co-investigator is on call for study patients.
- The PCP on L&D will call the research coordinator/call physician by phone or by text message that a study patient arrived on L&D for her birth.
- The research coordinator will review the list of admitted patients to L&D twice a day (8 AM and 4 PM) and once daily on Mother Baby Unit and Ob-Special care (Ob-Gyn wards) to identify enrolled study patients. This modality has been used with other studies in the department of Ob-Gyn and has been successful.

*Randomization*

- University of Utah coordinators will have access to UNM's REDCap to obtain randomization and enter any data collected for their participants.
- The research coordinator will access REDCap to obtain the randomization assignment for study patients (enrolled antepartum or on L&D not in labor) shortly after admission to L&D for a birth. The reproductive health physician on call will be notified
- For patients enrolled postpartum, the research coordinator will randomize the patient as soon after consent is signed or verbally agreed to and within 22 hours after birth to ensure implant placement for those randomized to the immediate group within 24 hours. For those who verbally agree, we will make an effort to obtain written consent via mail, e-mail, or eConsent in the UNM HSC REDCap system.
- The reproductive health physician on call will be notified to ensure placement of the implant within 24 hours; after hours, the reproductive health physician on call will also have access to the randomization sequence and will notify the research coordinator of the subject's identification number.

**PROTOCOL TITLE: Effect of immediate versus standard postpartum insertion of the contraceptive implant on breastfeeding outcomes**

*Implant insertion*

- The implant will be placed in accordance with the Federal Drug Administration (FDA) label instructions and only by providers who have completed the Merck training and are certified to insert the implant by Merck.
- Those allocated to the immediate group will obtain their implant in the hospital, by residents with attending supervision, fellows, attendings or certified nurse-midwives, and by obtaining the implant through the hospital pharmacy or the implants from the Family Medicine grant or LARC Mentoring Program for UNM participants.
- For those randomized to the standard insertion group, the implant will be provided in clinics as per clinic protocol. For UNM participants without insurance or those whose insurance does not cover immediate implant insertion, a limited number of implants (33) will be provided through the Family Medicine grant and additional implants will be available via the LARC Mentoring Program. UNM and University of Utah have established a process to enter all clinical study data via REDCap.

*Follow-up procedures:*

A research staff will keep a record of contact information for all participants. The staff will schedule visits for standard insertions at 4 weeks postpartum, will contact care provider to let them know the patient is participating in the study and the date of the appointment for the implant insertion. We will schedule standard insertion at 4 weeks postpartum in order to have a 2 week period to reschedule the participant if necessary. UNM appointments can be made at the Center for Reproductive Health Clinic (CRH) for increased convenience and to improve follow up if a participant cannot return to her antepartum clinic.

Research staff will contact participants randomized to the standard insertion group one week before the appointment to remind her of her appointment and will contact the care provider by a message in the EMR to let them know they date of the appointment for the implant insertion. Research staff will coordinate any necessary appointment rescheduling. Research staff will track this information for the purpose of the study CONSORT flow diagram.

Utah's research coordinators will have access to UNM's REDCap and will randomize and enter baseline data. They will also enter the study participants contact information (phone number or email) which is how they will receive the follow up study questionnaires.

UNM will call UNM participants and Utah will call Utah's participants for the follow up for the contact periods at 2, 4, 8, 12, and 24 weeks postpartum will be made by each site's research team to their respective study participants by phone calls, text messages or email. The text message and the emails will include a link to REDCap to access the follow up questionnaire to be completed by the participant. When/if the patient is contacted through phone call the UNM and Utah research staff will only contact their respective participants for completion of the questionnaires in REDCap.

**PROTOCOL TITLE:** Effect of immediate versus standard postpartum insertion of the contraceptive implant on breastfeeding outcomes

The questionnaires will contain data about breastfeeding, postpartum depression, and sexual function. A paper diary will be provided to aid the participant in daily recording of data. We will also include a retrospective data collection instrument to account for those we miss at the primary data collection points for breastfeeding information. If the primary questions have been answered either prospectively or retrospectively, then they get the normal prospective survey. If participants do not meet this criteria or if they miss a previous survey, then they will receive a retrospective survey. The diary will be collected at 2, 4, and 8 weeks. If possible, 2-3 good phone numbers will be obtained as well as addresses for each participant. Participants will have a phone number to contact study personnel at their specified site during standard work hours: Monday-Friday 8am- 4:30 pm with any concerns or adverse events. If they call after-hours, a voicemail system will be available, and the participant will be contacted the next working day.

*Data collection instruments*

Data collection instrument	Manner of collection	Timing	Included data
Enrollment form	Medical chart review  In-person, telephone and/or online via UNM's REDCap	After delivery  At enrollment	Participant & neonate medical history, delivery details  contraceptive history, contraceptive bridge-methods, lactation history, lactation and work expectations
Contraceptive Counseling Survey	In-person, telephone and/or online via UNM's REDCap	At enrollment and 4 weeks postpartum	Satisfaction with contraceptive counseling
Breastfeeding Survey	In-person, telephone and/or online via UNM's REDCap	2, 4, 8, 12, 24 weeks postpartum	Breastfeeding continuation, exclusivity, reasons for discontinuation if applicable, infant weight, resumption of intercourse, and satisfaction with contraception
EPDS	In-person, telephone and/or online via UNM's REDCap	2, 4, 8 weeks postpartum	Postpartum depression scale
FSFI	In-person, telephone and/or online via UNM's REDCap	4, 8, 12 weeks postpartum	Sexual function scale

PROTOCOL TITLE: Effect of immediate versus standard postpartum insertion of the contraceptive implant on breastfeeding outcomes

Bleeding diary	Paper or UNM's REDCap	Reviewed at 2, 4, 8 weeks. Collected at 2, 4, and 8 weeks	Bleeding patterns Side effects
Retrospective Breastfeeding Survey	In-person, telephone and/or online via UNM's REDCap	2, 4, 8, 12, 24 weeks postpartum	Breastfeeding continuation, exclusivity, reasons for discontinuation if applicable, infant weight, resumption of intercourse, and satisfaction with contraception
Retrospective Breastfeeding Discontinuation Chart Review Form	Medical Chart Review	Up to 1 year pp	Breastfeeding continuation if no response from survey. Infant feeding data as clinically described in the infant chart up to 1 year* postpartum may be collected if no response to survey and no data is available in the patient's chart.
Retrospective Contraceptive Use Chart Review	Medical Chart Review	Up to years pp*  *Nexplanon can be used for up to 5 years after insertion	Nexplanon use at any of the timepoints (2, 4, 8, 12, 24 weeks postpartum). We will review the mother's chart up to 5 years postpartum if contraceptive use data is not obtained from surveys or available from chart review within the first year postpartum.

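### Section 12.2 gives the after-hours on-call physician, a co-investigator, access to the randomization sequence, and nothing in the plan says upcoming allocations are hidden from those who enrol.

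*Combined protocol and SAP*

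**What the plan says.** Section 12.2 describes two routes to an allocation.

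- **Working hours.** "The research coordinator will access REDCap to obtain the randomization assignment for study patients". Utah coordinators use the same REDCap system for their own participants.
- **After hours.** "the reproductive health physician on call will also have access to the randomization sequence and will notify the research coordinator", the notification being of the participant's study number.

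On who covers which hours, section 12.2 says of the providers on the labour ward: "They will notify the research coordinator who will carry a phone during working hours". It continues: "After hours (nights and weekends), the research cell will forward to the reproductive health on-call fellow or attending". It also says: "A calendar will specify which co-investigator is on call for study patients".

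For women enrolled after delivery, the coordinator is named as the person who randomises. This happens once consent is signed or verbally given, and "within 22 hours after birth to ensure implant placement" in the immediate arm by 24 hours.

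Sections 4.1, 12.2 and 20.1 allow either the coordinator or a study co-investigator to explain the study, check eligibility and take consent. Section 21.3 also refers to a co-investigator who recruits.

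**The concern.** Section 3.1 justifies a randomised design by its protection against bias from treatment assignment, and names selection bias. That protection depends on the person who enrols not knowing what the next woman will receive. Once assigned, implant timing is plain to the woman and to staff, so concealment before assignment is the safeguard available at enrolment.

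Someone who can read the list and also decides whom to approach, or whom to find eligible, can steer women towards or away from an arm, even without intending to. In this trial that could make the arms differ in their likelihood of continuing to breastfeed at 8 weeks, which is the primary endpoint. The non-inferiority conclusion could be distorted either way.

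**Working it through.** The plan gives no figure on this point, so the check compares the passages.

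1. **What is granted.** The coordinator's route ends in an *assignment*, one result for one woman. The on-call physician's route is access to the *sequence*, which in ordinary use means the ordered list. Section 12.2 uses different words for the two roles and does not say they mean the same thing.

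2. **Who receives it.** The on-call role is a fellow or attending available around the clock, whose stated task includes making sure that randomisation happens. The calendar sentence shows that this person is a co-investigator.

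3. **Whether that person may enrol.** Sections 4.1, 12.2 and 20.1 permit a co-investigator to screen and consent. No sentence excludes the co-investigator who is on call.

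4. **Whether other text restores concealment.** Section 3.1 offers a general rationale for randomised trials and no procedure. For postpartum enrolments, section 12.2 puts consent before randomisation. That protects a woman's consent from her own drawn result, but it does not hide the next allocation from someone who can read the list. The available text does not say who generates the list, where it is held, or whether blocks or strata are used. It contains no statement that later allocations are hidden from either coordinators or physicians.

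5. **Whether the roles could meet in practice.** Postpartum women must be randomised within 22 hours of birth, and calls outside working hours go to the on-call physician. As an assumption, take the coordinator's hours to be those of the participant contact line, "during standard work hours: Monday-Friday 8am- 4:30 pm". A birth at 10:00 on Sunday reaches 22 hours at 08:00 on Monday. Every birth from Friday 16:30 to Sunday 10:00 would then have its whole window outside coordinator hours. The plan leaves room for on-call enrolment but does not describe it.

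6. **Whether the exposure can be sized.** On the same assumed hours:
   - Coordinator time is 5 × 8.5 = 42.5 hours of the 168 in a week, so 168 − 42.5 = 125.5 hours (125.5/168 = 74.7%) are after hours.
   - The stricter count from step 5 is 7.5 + 24 + 10 = 41.5 hours (41.5/168 = 24.7%).
   - If a coordinator must always present the study first, on-call enrolment could be zero.

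   These are shares of clock time, not of women. The documents do not say how many women would be enrolled after hours, by whom, or how any selection would relate to breastfeeding. The result is too open to turn into a bias or an error rate.

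**The case against.** The strongest defence is that the point turns on one word. Elsewhere the plan describes drawing an assignment through REDCap. The word *also* in the on-call sentence suggests that the physician gets the access the coordinator already has, and the duty to report the study number fits a backup draw better than an open list. This is a plausible reading. It does not settle the matter, because the text never says that the REDCap function shows one assignment at a time, and a reader cannot tell which meaning was intended.

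The second defence is that on-call enrolment is inferred. Sections 12.2 and 20.1 have the coordinator present the study before a co-investigator takes part. The on-call duties described are randomisation and implant placement. The after-hours contact described is about a woman already in the study: "The PCP on L&D will call the research coordinator/call physician by phone or by text message that a study patient arrived on L&D". Section 20.1 expects most women to consent antenatally, and the coordinator is the named randomiser for postpartum enrolments. Utah is described only with coordinator access. A woman whose window falls wholly outside coordinator hours might simply not be enrolled. All of this stands and narrows the exposure. It does not remove it, since co-investigators are expressly allowed to take consent.

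The third defence is that the contact-line hours are borrowed. They belong to a participant phone line that goes to voicemail, not to the forwarded research phone. That is correct, and the times in the working are therefore conditional. The conclusion does not depend on them.

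**Conclusion.** The concern holds as a flaw in the written safeguard. The plan does more than leave concealment unmentioned: it grants access which, followed literally, would remove concealment for any woman enrolled by the physician who holds it. This conclusion joins three statements in the plan (access, co-investigator status, and permission to enrol) with the absence of any statement that upcoming allocations are hidden.

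A reader might infer that allocations were in fact seen in advance, or that enrolment was steered. The documents do not support that. They describe no such event and no enrolment by the on-call physician, and the word *sequence* may mean only the REDCap draw.

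A reader might also want a figure for the inflation of the one-sided 5% error, or might conclude that the effect is small because few women are exposed. Neither is supported. The exposed share could be zero or substantial depending on how the text is read, and neither the strength nor the direction of any selection has a source in the documents. Selection favouring the immediate arm would make a false finding of non-inferiority more likely, while selection against it would make a true one harder to show.

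The text should be changed because the ambiguity touches a basic protection of the design and is cheap to remove.

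**What to change.** In section 12.2, Randomization, replace the grant of access to the sequence with a statement that the on-call physician obtains the assignment through REDCap. Then add that:

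- REDCap releases one time-stamped assignment per woman, only after eligibility and consent (written or verbal) have been recorded;
- nobody who screens, consents or inserts implants can view the allocation list.

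If women have already been randomised, report who had access to the list and how many assignments were drawn after hours, so that readers can judge the matter.

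The cost is one or two sentences and a setting of REDCap user rights. Coordinators at both sites already randomise through REDCap, so no new system is needed. The downside is that on-call physicians need randomise-only REDCap logins that work after hours. Sample size, endpoints and clinical procedures do not change.
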